A Prospective Multicenter Randomized Controlled Clinical Study to Investigate the Safety and Effectiveness of the RECELL® System Combined with Meshed Autograft for Reduction of Donor Skin Harvesting in Soft Tissue Reconstruction

Investigational Plan

Study Number: CTP007
Device: RECELL® Autologous Cell Harvesting Device
Study Type: Pivotal Study
IDE Reference Number: 13053
Date: October 30, 2020 / Revision 2
Sponsor: AVITA Medical
[name]
[name]

PRINCIPAL INVESTIGATOR'S STATEMENT

This statement is to certify that I have received the above-referenced investigational plan, which has been approved for initiation at my investigational site by the Institutional Review Board. As Principal Investigator, I will ensure that all personnel who have been delegated responsibilities for this study will be trained on the investigational plan and associated responsibilities prior to study participation. I agree to conduct this clinical study in compliance with the investigational plan and applicable requirements of the U.S. Code of Federal Regulations (21 CFR Parts, 50, 54, 56, 812 and 45 CFR Part 46).

Print Name: _____
Principal Investigator

Signature: _____ Date: _____
Principal Investigator

PROTOCOL SYNOPSIS

Title	A Prospective Multicenter Randomized Controlled Clinical Study to Investigate the Safety and Effectiveness of the RECELL® System Combined with Meshed Autograft for Reduction of Donor Area in Soft Tissue Reconstruction
Protocol No.	CTP007
Phase of Study	Pivotal Study
Intended Use	The RECELL® Autologous Cell Harvesting Device is indicated for use in combination with meshed autografting for treatment of acute full-thickness skin defects such as degloving, crush, laceration (including pretibial), and surgical wounds (e.g., flap donor, skin cancer resection, post-debridement for cellulitis or infection).
Primary Objective	To evaluate the safety and effectiveness of the RECELL Device when used as an adjunct to meshed autografts in patients undergoing reconstruction of skin defects not associated with a burn injury.
Planned Enrollment	
A minimum of 65 subjects will be enrolled and randomized in the study to evaluate the coprimary endpoints.
 
This study utilizes an adaptive design with planned sample size re-estimation in order to maintain adequate conditional power. The maximum enrollment will be 126 subjects.

Number of Trial Centers	Up to 20 trial centers in the United States (US) may participate.
Clinical Justification/Benefit	Use of RECELL as an adjunct to autografts meshed more widely than conventional meshed autografts will allow for reduction in donor skin harvesting required for autografting. Donor site morbidity, including pain, infection and delayed healing, are reduced for smaller donor areas; therefore, reduction of donor skin harvesting offers clinical benefit.
Investigational Treatment	Skin cell suspension prepared using the RECELL Device will be applied over autografts meshed more widely than a standardized comparator.
Control Treatment	Conventional autografting
Study Design	
This is a prospective randomized within-subject, blinded evaluator, multicenter controlled study to compare the clinical performance of conventional autografting with and without skin cell suspension on acute nonburn full-thickness skin defects.
 
Patients with a total body surface area (TBSA) acute skin defect up to 50% (inclusive) will be considered for participation in this study. An autografting plan for closure of the skin defect will be developed and documented in accordance with investigators' standard of care. Two comparable contiguous or non-contiguous areas, each at least 80 cm² in size will be identified as study treatment areas and labeled as Area A and Area B. These areas will be randomly assigned to autografting treatment consistent with the Investigator's pre-identified and documented autograft plan (Control) or to receive RECELL treatment in combination with an autograft meshed more widely than identified in the pre-specified autograft plan. For example, if the autografting plan calls for a 2:1 meshed autograft, this will form the Control and will be compared to an area treated with 3:1 meshed autograft and RECELL. The donor site(s) for skin harvested for the RECELL and Control treatments will be measured (area, cm²) and documented. The two study treatment areas will be compared with respect to healing characteristics, the amount of donor skin harvesting required and safety-related adverse events.
 
Treatment-area healing will be evaluated via direct visualization by the treating investigator (unblinded) and by a qualified clinical study team member blinded to

	
treatment allocation (i.e., Blinded Evaluator). The blinded assessment will serve as the primary healing assessment.
 
Donor expansion associated with treatments, and incidence of healing, will be evaluated 8 weeks after treatment for the purposes of a regulatory application (PMA supplement) for market approval of RECELL for this clinical indication. During the regulatory phase of the study, there will be follow-up visits at 1, 2, 4, 6, 8, 10, 12 and 26 weeks to evaluate the safety and effectiveness of RECELL for this indication, with durability confirmed at Week 26. Treatment-related and serious adverse events will be reported through Week 26. Participants will be seen for longer-term follow up at Weeks 36 and 52 to collect additional longer-term outcome data for publication.
 
During the early assessments, the preferred method is in-person clinical visits, however (if necessary), the follow-up visits may be conducted remotely (e.g., via telemedicine) with the exception of Week 8 and the confirmation of healing visit.
 
At all visits, subjects' study treatment areas will be documented photographically using standardized digital photography. Scar outcomes will be evaluated using the Patient and Observer Scar Assessment Scale (POSAS) questionnaire, which includes components for both the Blinded Evaluator and the subject. Subjects will be asked which treatment area they are more satisfied with (prior to unblinding), and then after unblinding, they will be told how much donor skin was associated with each treatment and the question of treatment preference will be asked again.
 
Data from this clinical investigation will be summarized in a Clinical Study Report (CSR) and presented to the Food and Drug Administration (FDA) once all subjects have completed their Week 26 visit. All available data, including Week 52, for subjects who have completed the study at that time will be included in the report. The CSR will be amended once all subjects have completed the study

Co-primary Effectiveness Endpoints	
 • Healing at (or prior to) 8 weeks post-treatment. Healing is defined as complete closure characterized by 100% skin re-epithelialization without drainage, confirmed at two consecutive study visits at least 2 weeks apart by direct visualization by a Blinded Evaluator. The incidence of healing is hypothesized to be non-inferior for RECELL-treated areas as compared to Control areas. • Ratio of actual expansion ratios. The actual expansion ratio, computed as the ratio of measured treated area to the measured donor site area, will be calculated separately for RECELL and Control (including donor skin needed for secondary treatments). The actual expansion ratios will be compared as a new ratio (ratio of ratios). The actual expansion ratio achieved with the use of RECELL is hypothesized to be superior to the actual expansion ratio associated with the Control.
Safety Evaluations	
Safety will be evaluated in terms of long-term durability, scar outcomes and treatment-related adverse events.
 
Safety variables that will be compared between the two treatments are:
 
 1. Delayed healing/non-healing 2. Infection 3. Allergic response to trypsin 4. Treatment area durability 5. Scar outcomes for which surgical intervention is determined to be medically necessary 6. Pain 7. Treatment-related and serious adverse events

Additional Data Collection	
 1. Investigator's (unblinded) assessment of healing at study treatment areas and donor site(s) 2. Scar outcomes reported by the Blinded Evaluator and patient (blinded) using the POSAS. 3. Effectiveness of treatment blinding for the Blinded Evaluator at Week 8. 4. Effectiveness of treatment blinding for the subject at Week 26. 5. Subject (or parent/guardian) treatment preference at Week 52. 6. Investigator treatment preference at Week 52.
Inclusion Criteria	
Subjects must meet all the following criteria to be eligible for participation:
 
 1. The patient requires autografting for treatment of an acute full-thickness skin defect (e.g., trauma- or surgery-related). 2. The maximum area requiring autografting is 50% TBSA. 3. Two comparable areas requiring autografting, each at least 80 cm² (or 160 cm² contiguous), excluding face and genitalia. When hands, feet or joints are included in the treatment areas, comparability of treatment areas means that each area (RECELL and Control) must include the same contralateral joint and/or hand/foot. 4. The patient is at least 5 years of age. 5. The patient (or parent/guardian) is willing and able to comply with all compulsory study procedures and visit schedule. 6. The patient (or parent/guardian) agrees to abstain from any other treatment of the study areas for the duration of his/her participation in the study (1 year). 7. The patient agrees to abstain from enrollment in any other interventional clinical trial for the duration of his/her participation in the study (1 year). 8. In the opinion of the investigator, the patient and/or guardian must be able to: 
 a) Understand the full nature and purpose of the study, including possible risks and adverse events, b) Understand instructions, and c) Provide voluntary written informed consent.
Exclusion Criteria	
Subjects who meet any of the following criteria are not eligible for participation:
 
 1. Not able to understand English or Spanish. 2. The area requiring autografting sustained a burn injury. 3. The treatment area has previously failed to heal subsequent to surgical intervention for closure. 4. The patient is unable to follow the protocol requirements. 5. The patient has a condition that in the investigator's opinion may compromise patient safety or trial objectives. 6. Current use of medications that in the investigator's opinion may compromise patient safety or trial objectives. 7. The patient has a known hypersensitivity to trypsin or compound sodium lactate for irrigation (Hartmann's) solution. 8. The patient is pregnant or breast-feeding (pregnancy test should be performed in accordance with local institutional requirements). 9. Life expectancy is less than 1 year.

Study-specific procedure highlights	
 The study treatment areas will be prepared using standard surgical techniques. The surgeon will identify and document an autografting plan for areas to be autografted [i.e., identifying areas to receive sheet graft, minimally perforated graft, and meshed graft (1:1, 2:1, 3:1)]. Subsequent to development of the autografting plan, two comparable treatment areas (with similar plans) will be identified as study treatment areas A and B by either bisecting one contiguous area or identifying two similar non-contiguous areas and photographed after appropriate demarcation with a surgical marker. The randomization envelope is opened to identify which area (A or B) is Control and which is RECELL. The autografting plan is followed as originally documented for the area assigned to Control The originally documented autografting plan is amended as follows for the area assigned to RECELL: 
 Sheet, minimally perforated or 1:1 will instead be 2:1 mesh and RECELL 2:1 mesh will instead be 3:1 mesh and RECELL 3:1 mesh will instead be 4:1 mesh and RECELL Donor site(s) for skin allocated to RECELL and Control study treatment areas will be measured (area, cm²) and documented.
Statistical Considerations	
The sample size was determined so as to provide at least 80% probability that both co-primary endpoints will be met. Primary effectiveness will be assessed on the following two analysis sets: Intent to treat population (ITT) – All those enrolled into the study who are randomized; and Per protocol population (PP) – ITT subjects who receive both study treatments and have no major protocol deviations.
 
The hypotheses to be tested for the co-primary endpoint of Confirmed Healing is the proportion of RECELLtreated autograft area healed prior to or at the 8-week visit is non-inferior to the standard of care Control treated graft area.
 
For the co-primary effectiveness endpoint for confirmed treatment area closure, the hypothesis test of non-inferiority will be one-sided with a 2.5% significance level; for the endpoint of relative reduction in donor site area, the hypothesis test of superiority will be one-sided with a 2.5% significance level, all other statistical tests will be two-sided at the 5% significance level, unless otherwise noted.
 
An unblinded conditional power calculation and sample size re-estimation will be conducted once approximately 50% of total enrollment has been evaluated for the primary effectiveness endpoint; i.e., 33 subjects have been randomized and reached the Week 8 visit (or healing confirmatory visit) or would have reached the Week 8 visit had they not prematurely withdrawn.
 
To account for missing data and/or loss of subjects from the PP analysis population, the sample size was increased to 65 patients which represents an attrition rate of approximately 10%.

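### Does evaluating donor expansion at Week 8 wrongly leave donor skin for later re-grafts out of the co-primary ratio?

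*Combined protocol and SAP*

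**What the plan says.** All the available text is the Protocol Synopsis.

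- **Study Design** gives the only time for this endpoint: "Donor expansion associated with treatments, and incidence of healing, will be evaluated 8 weeks after treatment". Visits continue to Week 26 for the regulatory phase and to Week 52 overall. The study report is to be "presented to the Food and Drug Administration (FDA) once all subjects have completed their Week 26 visit".
- **Co-primary Effectiveness Endpoints** limits healing in time ("Healing at (or prior to) 8 weeks post-treatment"). The expansion ratio is treated area over donor area, taken separately for each treatment, "including donor skin needed for secondary treatments". That definition states no window.
- **Study-specific procedure highlights** lists donor measurement after the grafting steps: "Donor site(s) for skin allocated to RECELL and Control study treatment areas will be measured (area, cm²) and documented".
- **Statistical Considerations** places the interim look when "33 subjects have been randomized and reached the Week 8 visit (or healing confirmatory visit" is satisfied, and tests expansion for superiority at a one-sided 2.5% level.
- **Study Design** also says of subjects, before the second preference question, that "they will be told how much donor skin was associated with each treatment".

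**The concern.** The two co-primaries stand side by side. One carries a time limit and the other does not, yet the untimed one includes an item that accrues over time. An area still open at Week 8 is an obvious candidate for a second graft, and that harvest would fall after the visit. Non-healing, durability and medically necessary scar surgery are all listed safety variables, so late surgery is foreseeable.

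Reduced donor harvesting is the claim in the trial's title. If one analyst stopped counting at Week 8 and another at Week 26, they could report different savings from the same subjects. If late re-grafts were concentrated in the more widely meshed RECELL areas, a Week 8 ratio would flatter RECELL. The donor totals told to subjects would share the same unstated window.

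**Working it through.** **1. The text.** Three readings of the window can be compared with the rest of the plan.

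| Window | Stated for donor expansion? | Same clock as healing co-primary? | Complete at the interim? |
|---|---|---|---|
| Week 8 | Yes, Study Design | Yes | Yes |
| Week 26 | No | No | No |
| Week 52 | No | No | No |

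Only Week 8 fits throughout. The interim's alternative of a confirmatory visit follows from the healing definition, which needs two visits at least 2 weeks apart. It says nothing about donor skin.

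**2. What could be missed.** There is no planned figure to reproduce, because the documents give no late re-graft rate, extent or mesh. The following is an illustration only.

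Inputs: the 2:1 to 3:1 step (Study-specific procedure highlights). Assumptions: 100 cm² per area, nominal mesh, late re-grafts at the Control mesh, skin for the cell suspension ignored, and failures independent between a subject's two areas.

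- Initial donor skin: Control 100/2 = 50; RECELL 100/3 = 33.33. Week 8 ratio of ratios = 50/33.33 = 1.50, a saving of 1 − 1/1.50 = 33%.
- A whole-area late re-graft adds 50 to the area concerned. Subject-level ratios are then 50/33.33 = 1.5 (neither area), 50/83.33 = 0.6 (RECELL only), 100/33.33 = 3.0 (Control only) and 100/83.33 = 1.2 (both).
- With late rates pR and pC, the pooled ratio is (50 + 50·pC)/(33.33 + 50·pR). For quarter-area re-grafts, 50 is replaced by 12.5 in the added terms.

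Worked case, 5% on each side, whole area:

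- Pooled: 52.50/35.83 = 1.47.
- Arithmetic mean: 0.9025×1.5 + 0.0475×3.0 + 0.0475×0.6 + 0.0025×1.2 = 1.53.
- Geometric mean: exp(0.9025·ln 1.5 + 0.0475·ln 3.0 + 0.0475·ln 0.6 + 0.0025·ln 1.2) = 1.48.
- Median: 1.50, since 90% of subjects sit at 1.5 and only 5% lie below it.

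| Late rate, RECELL / Control | Pooled, quarter area | Pooled, whole area | Geometric mean, whole | Arithmetic mean, whole | Median, whole |
|---|---|---|---|---|---|
| 10% / 2% | 1.45 | 1.33 | 1.39 | 1.44 | 1.50 |
| 5% / 5% | 1.49 | 1.47 | 1.48 | 1.53 | 1.50 |
| 5% / 20% | 1.55 | 1.67 | 1.65 | 1.75 | 1.50 |

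**3. Direction.** The pooled ratio stays at 1.50 when 50 + 50·pC = 1.5 × (33.33 + 50·pR), that is, when pC = 1.5·pR. Below that, a Week 8 cut-off overstates the saving; above it, the saving is understated. The arithmetic mean already moves the other way at equal rates. The design is within-subject and the definition forms a new ratio from two ratios, so a per-subject summary is at least as natural as a pooled one.

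**4. Distance to no advantage.** The pooled ratio equals 1 when 50 + 50·pC = 33.33 + 50·pR, so pR − pC = 1 − 2/3 = 33 points. For the other steps it is 1 − 1/2 = 50 points (1:1 to 2:1) and 1 − 3/4 = 25 points (3:1 to 4:1).

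**The case for a change.** The strongest case for acting is that evaluating an endpoint at a visit is not quite the same as saying which harvests count, and that one sentence would settle it. For a single subject the stakes are real: with 80 cm² areas at 2:1 against 3:1, donor skin is 40 against 26.7 cm². A late RECELL re-graft of a quarter of the area adds 10 cm² and takes the ratio from 1.50 to 40/36.7 = 1.09. Beyond 33% of the area the advantage is gone. No separate step for measuring later harvests is described either, so a later supportive analysis might lack data. The bar on other treatment of the study areas in the Inclusion Criteria does not dispose of this, because the endpoint itself expects secondary treatments.

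These points stand as far as they go. The window is not written into the endpoint definition, and a ratio counting donor skin through Week 26 would be informative. But reaching a different co-primary value requires an analyst to set aside the only time the synopsis gives. The single-subject effect also dilutes in a group: if 5% to 20% of subjects had a late RECELL-only re-graft of 25% to 100% of the area, the geometric mean would fall from 1.50 to between 1.48 and 1.25. The preference question is listed under Additional Data Collection for Week 52 and does not enter the co-primary.

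**Conclusion.** No change is needed. The plan leaves a detail unstated, and the natural reading fills it: secondary-treatment donor skin is counted up to the Week 8 evaluation, for both areas of the same subject on the same clock. This is a fair trade-off. It gives up late harvests in exchange for an endpoint that is complete at the interim and shares its time point with healing.

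Late failures do not disappear. An area not healed by Week 8 counts against its treatment in the other co-primary, which must also succeed. Later breakdown and late surgery are captured by the safety variables, and the report waits for Week 26.

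In the 2:1 to 3:1 illustration, the ratio with late whole-area re-grafts ranges from 1.33 to 1.75 around the Week 8 value of 1.50, depending on the assumed rates and the summary. It can move either way, so no bias is shown. These figures rest on assumed rates and nominal mesh, whereas the endpoint uses measured areas. They concern point estimates only: no standard deviation is available, so the effect on the superiority test was not assessed. A window may also be stated in parts of the plan outside the synopsis.

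### Low-cost improvement: reporting of treatment-related and serious adverse events stops at Week 26, so the 52-week report could not separate no late events from late events not collected

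*Combined protocol and SAP*

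**What the plan says.** All references are to the Protocol Synopsis.

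- **Reporting window (Study Design).** "Treatment-related and serious adverse events will be reported through Week 26".
- **Visits (Study Design).** In the regulatory phase "there will be follow-up visits at 1, 2, 4, 6, 8, 10, 12 and 26 weeks", with durability confirmed at the last of these. After that, "Participants will be seen for longer-term follow up at Weeks 36 and 52 to collect additional longer-term outcome data for publication". Inclusion Criteria items 6 and 7 give participation as 1 year.
- **Where late data go (Study Design).** The first CSR is prepared once every subject has passed Week 26. On later data: "All available data, including Week 52, for subjects who have completed the study at that time will be included in the report". Then: "The CSR will be amended once all subjects have completed the study".
- **Role of these events.** Study Design says: "The two study treatment areas will be compared with respect to healing characteristics, the amount of donor skin harvesting required and safety-related adverse events". Safety Evaluations says: "Safety will be evaluated in terms of long-term durability, scar outcomes and treatment-related adverse events". It lists treatment-related and serious adverse events as item 7 of the variables to be compared between treatments, and gives that item no time window of its own.
- **What is expressly placed after Week 26.** At all visits, "study treatment areas will be documented photographically using standardized digital photography". Additional Data Collection adds subject and investigator treatment preference at Week 52.

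**The concern.** The plan follows subjects for a year and sends the later data to the CSR, but one of its listed safety variables has a reporting window that ends halfway. Safety Evaluations gives no window for item 7, so the Week 26 sentence is the only one that applies.

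The amended CSR, and any publication built on it, could then present outcomes at 52 weeks beside adverse events at 26 weeks. An empty table after Week 26 would be uninformative. Photographs may show that a treatment area has changed, but they do not record the type of event, its seriousness or its relation to treatment. At stake is the completeness of the descriptive long-term safety record, not the primary analysis.

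**Working it through.** The plan gives no figure to reproduce, because the point concerns a time window. The check has four steps.

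**1. Follow-up outside the window**
- Visits inside: Weeks 1, 2, 4, 6, 8, 10, 12 and 26, which is 8. Visits outside: Weeks 36 and 52, which is 2. Share outside: 2/10 = 20%.
- Weeks outside: 52 − 26 = 26, or 26/52 = 50%.
- Enrollment limits (Planned Enrollment): 65 minimum, 126 maximum.
- Subject-years outside = n × 26/52. For 65 subjects this is 32.5, and for 126 it is 63, with no attrition.

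**2. What late recording would offer if no events were seen**

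With zero events in n subjects, the one-sided 95% upper bound on per-subject risk is 1 − 0.05^(1/n). Each subject has one area under each treatment, so the same n applies to RECELL and to Control if all subjects receive both treatments and are followed.

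| Subjects followed to Week 52 | Upper bound |
|---|---|
| 65 (minimum, no attrition) | 4.50% |
| 126 (maximum, no attrition) | 2.35% |
| 58 (65 × 0.9 = 58.5, rounded down) | 5.03% |
| 113 (126 × 0.9 = 113.4, rounded down) | 2.62% |

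The last two rows assume that the approximate 10% attrition in Statistical Considerations also applies to late follow-up. The plan uses that figure for missing data and loss from the per-protocol population, not for Weeks 27 to 52.

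**3. Whether late events could support a formal comparison**

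In a two-sided exact paired test at 5%, five discordant subjects all in one direction give p = 2 × 0.5^5 = 0.0625, and six give p = 2 × 0.5^6 = 0.031. So at least six are needed, all on the same side. The documents give no late-event rate, so the risks below are assumptions. Expected subjects with a late event = n × risk.

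| Assumed per-subject late risk | n = 65 | n = 126 |
|---|---|---|
| 1% | 0.65 | 1.26 |
| 2% | 1.3 | 2.52 |
| 5% | 3.25 | 6.3 |

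Only the last cell reaches six, and nearly all of those events would have to fall on one treatment. A late comparison would be descriptive.

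**4. Whether other text closes the gap**
- The sentences on the CSR and its amendment govern which available data are reported. They do not extend the window for item 7.
- Infection, durability, scars needing surgery and pain are separate safety variables, and the Week 26 sentence does not name them. They might give partial late information, but the synopsis does not say that they are collected at Weeks 36 and 52.

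**The case against.** The strongest reply is that the window was chosen on purpose. Visits through Week 26 serve the safety and effectiveness evaluation for the regulatory application, durability is itself confirmed at Week 26, and the two later visits are for publication. That stands. A reader might infer that the plan contradicts itself or breaks a promise to compare events over the full year. The documents do not support this, because neither Study Design nor Safety Evaluations commits to a comparison through Week 52.

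A reader might also infer that no safety information at all will exist after Week 26, or that late events will certainly go unrecorded. That is too strong as well. The limit names only treatment-related and serious adverse events, four other safety variables are not expressly stopped there, and the sentence concerns reporting. The documents support only that the late record need not contain these events.

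Two further points stand. Serious events that cannot be assigned to one area add little to a within-subject comparison, and collecting all of them for another 26 weeks would cost more than two visit forms. The fix is narrowed for that reason. Finally, only the synopsis is available here, and a fuller adverse event section may say more.

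The reply does not answer the reporting problem. The later data are not confined to publication, since they also enter the CSR and its amendment, where their silence on this class of event could not be interpreted.

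**Conclusion.** This holds as a low-cost improvement, not as an error. As written, item 7 of the safety variables need not cover Weeks 27 to 52, although subjects are still being seen and their other late data are reported. The gain from closing the gap is a readable late record for this class of event and, if none occurred, the bounds in the working.

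The actual effect of the gap is unknown. The bounds assume that every subject counted is followed to Week 52 and that events between visits are recalled. The conclusion also assumes that no fuller adverse event section already extends the window. If one does, only the synopsis sentence needs aligning.

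**What to change.** Keep the Week 26 window for the adverse event analysis in the first CSR, and add after the existing sentence:

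*Treatment-related adverse events, and serious adverse events involving a study treatment area or donor site, occurring after Week 26 will be recorded at the Week 36 and 52 visits, and will be summarised descriptively by treatment through Week 52 in the CSR amendment.*

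Then check any fuller adverse event section for consistency with this wording.

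The cost is event forms, with seriousness and relatedness assessment, at two visits that already take place. Events between those visits depend on subject recall, and serious events away from the study and donor areas stay outside the added record unless they are treatment-related. The documents give no cost figure; calling the change low-cost rests on its needing no added visits or subjects and no change to sample size, power, significance level or the timing of the first CSR.

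### For non-serious local events outside safety variables 1–6, variable 7 compares the two areas only after a relatedness call that is not described as blinded, so it can reflect attribution as well as event rates

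*Combined protocol and SAP*

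**What the plan says.** The Protocol Synopsis, under Study Design, describes a "prospective randomized within-subject, blinded evaluator, multicenter controlled study". One area of each subject receives the planned autograft (Control). The other receives a more widely meshed autograft with RECELL.

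On event reporting, the same section says "Treatment-related and serious adverse events will be reported through Week 26".

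On assessors, it says "Treatment-area healing will be evaluated via direct visualization by the treating investigator (unblinded", and that a Blinded Evaluator also assesses healing: "The blinded assessment will serve as the primary healing assessment". The Blinded Evaluator also completes the observer part of the scar scale.

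Under Safety Evaluations, the framing sentence is "Safety will be evaluated in terms of long-term durability, scar outcomes and treatment-related adverse events". The list that follows is introduced by "Safety variables that will be compared between the two treatments are". It begins "1. Delayed healing/non-healing 2. Infection 3. Allergic response to trypsin 4. Treatment area durability", continues with scar outcomes needing surgery (5) and pain (6), and ends with "7. Treatment-related and serious adverse events". Variables 1 to 6 carry no relatedness condition.

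The text does not say who judges relatedness, whether that person is blinded, or whether the term refers to RECELL, to grafting, or to either. Nor does it say what happens to a non-serious event judged unrelated.

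**The concern.** Randomising two areas within one subject makes local event counts directly comparable: patient, surgeon, visit and follow-up are shared, and location alone says which treatment the event belongs to. No causality judgement is needed.

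Variable 7 adds one. A non-serious event enters the comparison only after it has been called treatment-related, and that call can be made with the allocation known. Both areas receive an autograft. A blister, haematoma or itching might be put down to the new device on one area and regarded as a routine feature of grafting on the other, or the reverse. If the two areas are treated differently in this way, the reported difference mixes event rates with attribution habits. It could show an excess on RECELL that is not there, or hide one that is.

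The plan guards the healing endpoint against knowledge of allocation by making a blinded assessment primary. It describes no such guard for variable 7.

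**Working it through.** The documents give no event rate, attribution rate or power for variable 7, so there is no figure to reproduce. The check has two parts: which events the filter reaches, and what unequal attribution would do.

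**1. Which events the filter reaches**

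- Serious events are reported whatever the causality, so they are not filtered.
- Events captured by variables 1 to 6 have no relatedness condition, so they are not filtered on the text.
- Non-serious local events outside variables 1 to 6 are reported only if judged treatment-related. These are the events at issue.

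**2. Effect of unequal attribution (illustration)**

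Inputs from the documents: minimum 65 and maximum 126 subjects (Planned Enrollment); two-sided 5% level for tests other than the co-primary ones (Statistical Considerations). Assumed inputs: the true proportion of subjects with such an event in an area, *p*, and the probabilities that an event is called related, *a*R (RECELL) and *a*C (Control).

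Reported rates: *r* = *p* × *a*R and *c* = *p* × *a*C.

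Paired comparison by the McNemar normal approximation, with the two areas taken as independent:

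- discordant proportions *r*(1 − *c*) and *c*(1 − *r*); difference *d* = *r* − *c*; sum *s*
- standard error under no difference √(*s*/*n*); otherwise √((*s* − *d*²)/*n*)

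Example with *p* = 0.20, *a*R = 0.80, *a*C = 0.60, *n* = 65:

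- *r* = 0.20 × 0.80 = 0.16; *c* = 0.20 × 0.60 = 0.12; *d* = 0.04
- *s* = 0.16 × 0.88 + 0.12 × 0.84 = 0.1408 + 0.1008 = 0.2416
- standard errors √(0.2416/65) = 0.0610 and √(0.2400/65) = 0.0608
- chance of a nominally significant difference: about 10%

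With a true rate of 20% in both areas:

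| Called related, RECELL / Control | Reported rates | n = 65: expected subjects; chance of significance | n = 126: expected subjects; chance of significance |
|---|---|---|---|
| 70% / 70% | 14% v 14% | 9.1 v 9.1; 5.0% | 17.6 v 17.6; 5.0% |
| 80% / 60% | 16% v 12% | 10.4 v 7.8; 10.0% | 20.2 v 15.1; 14.9% |
| 90% / 50% | 18% v 10% | 11.7 v 6.5; 25.4% | 22.7 v 12.6; 44.3% |
| 90% / 30% (extreme) | 18% v 6% | 11.7 v 3.9; 54.5% | 22.7 v 7.6; 83.0% |

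Over true rates of 10% to 30% and the 80/60 and 90/50 gaps, the chance of a false difference runs from 7.3% to 38.0% at 65 subjects and from 9.5% to 64.1% at 126. Swapping the two attribution rates gives the same probabilities with the opposite sign. Equal attribution keeps the 5% level but still under-reports events: 14% instead of 20% at 70%.

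Masking works the same way. True rates of 20% (RECELL) and 15% (Control), with 60% and 80% called related, give 0.20 × 0.60 = 0.12 and 0.15 × 0.80 = 0.12. A true 5-point excess disappears.

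**The case against.** Four stronger readings are tempting, and the documents do not support them.

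- *All non-serious local events are filtered.* They are not. Variables 1 to 6 cover the main local outcomes without a relatedness condition. Graft loss that affects closure also bears on healing, which has a blinded primary assessment, and donor skin used for secondary treatment enters the expansion ratio.
- *The unblinded treating investigator makes the call.* This is a natural inference, since no other assessor is named for it, but it is not stated.
- *Related means device-related.* The synopsis calls conventional autografting the Control treatment and speaks of two treatments. If the term covers grafting on either area, a graft complication on Control is also treatment-related, fewer events are removed and the asymmetry shrinks.
- *Nothing can be recovered later.* Study areas are photographed at every visit, so some visible events could be re-reviewed. Symptoms such as itching, and events that resolve between visits, could not be recovered reliably.

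In addition, the text considered here is essentially the synopsis, and definitions and causality rules may sit in other sections. The Study Design comparison also speaks of safety-related events, without a relatedness call. And every rate in the illustration is assumed; the residue outside variables 1 to 6 may be less frequent than 10% to 30%.

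These objections narrow the point and leave its size open. They do not remove it: no passage lifts the filter from variable 7, and none describes a blinded judgement of relatedness.

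**Conclusion.** The point holds for variable 7, restricted to non-serious local events outside variables 1 to 6. The reporting rule is stated, not missing, and applying it to a between-area comparison lets attribution enter where location alone would do. It should be changed, but it does not touch the co-primary endpoints.

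Size and direction are not determined by the documents. Under the assumed 80/60 gap and a 20% true rate, the effect at 65 subjects is modest (about 10% against 5%); with wider gaps or more subjects it is not. The conclusion assumes that whoever judges relatedness knows, or may know, the allocation. The probabilities also assume independent areas and a normal approximation, which is rough at these counts; correlation between areas would change the probabilities but not the reported rates.

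**What to change.** - Through Week 26, record every adverse event located at either study area, whatever the causality judgement, with its location (RECELL area or Control area).
- Make the paired comparison of all local events at the two study areas the main analysis for variable 7, with the treatment-related subset secondary.
- Define treatment-related (RECELL, grafting, or either), and state who judges it and whether that person is blinded. State also whether infection and pain are captured independently of that judgement.
- Record donor-site events too, since the clinical justification rests on lower donor-site morbidity. Link each to the RECELL or Control donor skin where the two are separable. Where they are not, summarise the events descriptively, outside the paired comparison.
- Leave the serious-event rule as it is. If other sections already require all of this, align the synopsis with them.

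The cost is protocol and form wording and some additional minor event entries, at visits where both areas are already photographed. One limitation remains: if unblinded staff detect and log the events, knowledge of allocation can still affect what is noticed and recorded.
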